Title: RVA Breathes: A Richmond City Collaboration to Reduce Pediatric Asthma Disparities

NCT #: NCT03297645

Document date: June 9, 2022

Document type: Statistical Analysis Plan

Statistical Analysis Plan RVA Breathes

We will explore the data using descriptive statistics (e.g., frequency distributions, contingency tables) prior to any hypothesis testing and consider transformation as appropriate.

Aim 1: We hypothesize that children in the two active interventions will achieve reductions in healthcare utilization (e.g., asthma-specific ED visits, hospital admissions) and school absences, and an increase in controller medication use (calculated from refill data from insurers) at post-treatment and follow-up than children in the comparator condition. Our primary outcome, healthcare utilization, will be defined as a composite of the frequency of asthma-related inpatient and ED visits. A composite variable (i.e., sum score) that takes into account the frequency of asthma-related inpatient and frequency of ED visits will be calculated for each participant. At baseline, historical data will be obtained to ensure that we have captured utilization for the 9 months prior to the baseline visit (i.e., utilization before the intervention begins). Our primary endpoint is the change in mean rate of ED/hospitalization in 9 months before to 9 months after RVA Breathes across groups. Generalized Linear Mixed Models (GLMM) will be used to determine within person changes in healthcare utilization across time, and then differences in healthcare utilization between groups (e.g., intervention vs. control). Thus, our main outcome is change in healthcare utilization at the individual level as an average of individuals. We will also *explore* differences in outcomes between the two active intervention conditions [(1) asthma education + home remediation + school intervention vs. 2) asthma education + home remediation] to determine the value of adding a school-based component. Differences in healthcare utilization (and other outcomes) will again be tested using a Generalized Linear Mixed Model (GLMM). GLMM models will be fit to multiple types of dependent variables including, Gaussian/Normal, Binomial, Poisson and Negative Binomial. The GLMM model fit will include a between-subject factor (Group, representing the control group and the two intervention groups) and will also include a random effect for the cluster (school). These models will be modified in longitudinal assessments by the inclusion of a within-subject factor (Time [pre, post]) and the interaction between Group and Time variables. The inclusion of the interaction terms allows for a formal test of differing courses between the groups over time. To account for seasonality and the impact of COVID-19, we will include sine and cosine functions of $x = 2\pi \cdot (\text{time} / \text{max(time)})$ covariates and COVID-19 impact as covariate in analyses. COVID-19 impact will be designated as March 13, 2020 and Covariate=0 for months before COVID-19 and Covariate=1 for months after COVID-19. We will adjust for multiple comparisons using the Holm-Bonferroni method. In addition to healthcare utilization, we will also consider changes in the secondary outcomes of asthma action plans and controller medication use between conditions.

Aim 2: We hypothesize that secondary outcomes (asthma control, symptoms, quality of life) of children in the intervention groups will be superior to those of the control group. These outcomes will be tested using the GLMMs described under Aim 1 utilizing the proper distribution and link functions for the outcome variable examined.

Aim 3: We hypothesize that intervention effects will be mitigated in families with caregivers with lower levels of asthma self-management skills at baseline, as well as in those with higher baseline levels of stress and depressive symptoms. These outcomes will also be tested using the GLMMs described under Aim 1 utilizing the proper distribution and link functions for the outcome variable examined that have been modified by the inclusion of an additional effects measuring caregivers' self-management skills, as well as stress and depressive symptoms. The inclusion of these covariates will allow us to adjust the intervention effects and increase the

generalizability of the intervention effects based upon caregivers' characteristics.

Sample size. From RVA Breathes baseline data, Group 1 children (full intervention: CHW + HH assessors + school) had a 9-month ED visit rate of 2.22 visits. Group 2 (CHW + HH, no school) had a 9-month ED rate of 1.89 visits, and Group 3 (control) had a 9-month ED rate of 1.68. We used recent published rates from a comparable study that considered changes in child asthma-related ED visits from 6 months prior to intervention to 6 months post-intervention (Johnston et al., 2019). In this study, the intervention group went from 2.0/6mo (pre) to 0.55/6mo (post) and the control group went from 1.3/6mo (pre) to 0.85/6mo (post). Thus, the intervention group had a 72% reduction $((2.0-0.55)/2.0 = 0.72)$ and the "control" group had a 35% reduction $((1.3-.85)/1.3 = 0.35)$.

Basing our numbers on these same rates, we would expect the following power estimates with 9-month follow up data: 14% for Groups 1 vs. 2, 97% for Groups 1 vs. 3, and 88% for Groups 2 vs. 3. Using alpha = .0167, we would assume average clusters of 10 in 24 schools for 240 enrolled participants. Allowing for 20% attrition, this would be 300 participants. Moreover, using a Poisson model for analyses, we would use a CVB (between-cluster coefficient of variation) instead of ICC. These analyses would use a CVB for G1 vs. G2 = 0.1331, for G1 vs. G3 = 0.1820, and for G2 vs. G3 = 0.0502.

Missingness. We will handle missing data in several ways. Health utilization is being reported by caregivers (self-report) and we are also receiving health encounter data from insurers and hospital billing systems. For families that have been lost to follow-up but have not asked to withdraw from the study, we will still receive and use their objective health encounter data. This will limit missingness related to our main outcomes when using encounter data. For self-report data, we will conduct a sensitivity analysis on raw data and examine patterns of missingness. We then will use a pattern-mixture model with multiple imputation from other available timepoints. We can then compare those analyses to analyses using objective health encounter data.

Missing Data and Participant Attrition Strategies:

The primary analysis will follow the approved statistical analysis plan, without any changes for missing data. After fitting this model, missing data patterns will be examined and their patterns will be examined, in particular looking for a monotone missing data pattern indicative of attrition. If, as expected, we find that there is a monotone pattern of missing data (i.e., once an individual misses an observation, they will be missing all subsequent observations), this will provide evidence that the missing completely at random (MCAR) and missing at random (MAR) assumptions may be violated. To examine the impact of monotone missing data, multiple imputation using a pattern-mixture model with control-based imputation will be utilized. We will create 50 imputed datasets for the outcomes and analyze them using the primary analysis model. The results from these 50 analyses will then be combined to derive an overall result. This will allow us to perform a sensitivity analysis to see how much bias the missing data causes.

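### The primary Group × Time contrast compares each arm with its own baseline but does not condition on the child's pre count; a baseline-adjusted analysis should be prespecified beside it

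*SAP*

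**What the plan says.** SAP, Aim 1 sets the endpoint as a change: "Our primary endpoint is the change in mean rate of ED/hospitalization in 9 months before to 9 months after RVA Breathes across groups". The pre count is to be available for every child: "historical data will be obtained to ensure that we have captured utilization for the 9 months prior to the baseline visit". It enters the model as part of the outcome, through "inclusion of a within-subject factor (Time [pre, post]) and the interaction between Group and Time variables", so each group has its own free baseline mean. On clustering, the GLMM "will also include a random effect for the cluster (school"); no child-level effect is named. The covariates for this analysis are sine and cosine season terms and "COVID-19 impact as covariate in analyses". Aim 3 adds caregiver skills, stress and depressive symptoms. No utilization covariate appears anywhere.

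SAP, Sample size reports baseline rates by arm. Group 1 "had a 9-month ED visit rate of 2.22 visits", Group 2 had 1.89, and "Group 3 (control) had a 9-month ED rate of 1.68". These are ED visits only, not the ED-plus-inpatient composite, and come without SDs or numbers of children. Neither document says how a baseline difference between arms will be handled.

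**The concern.** A change contrast subtracts the whole observed baseline gap, which is correct only if the whole gap would have persisted without treatment. Any part that would have faded appears as a larger fall in the arm that started higher. Here both active arms start above control, Group 1 furthest, so the tilt runs in the hypothesized direction.

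The documents give reasons to expect some fading. Protocol D2, 2.a requires an asthma event or steroid course in the last two years, and 2.d uses daily lists of children who are in the ED or hospital at the time. Some high pre counts should therefore fall back unaided. Even without selection, a chance gap fades unless each child's count is perfectly stable.

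Two things are at stake: how an active-vs-control estimate should be read given this baseline, and precision. A contrast that conditions on the child's pre count is less variable when the pre-post correlation is low to moderate.

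**Working it through.** **Inputs.** From SAP, Sample size: the three baseline rates; 24 schools averaging 10 children; alpha 0.0167; between-school CV (CVB) 0.1820 for Group 1 vs 3; and the cited study, where "the intervention group went from 2.0/6mo (pre) to 0.55/6mo (post") and control went from 1.3 to 0.85. Assumed, because the documents do not give them: pre-post correlation 0.15–0.67, 8 schools per arm, gamma-distributed school, child and child-period variation, and (step 4 onward) a 40% lower rate during COVID-19. Ratios below 1 favour the active arm.

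**1. The plan's own figures.** (2.0 − 0.55)/2.0 = 0.725 and (1.3 − 0.85)/1.3 = 0.346, the SAP's 72% and 35%. The planned Group × Time ratio is (1 − 0.72)/(1 − 0.35) = 0.28/0.65 = 0.43. The baseline ratios are 2.22/1.68 = 1.32 and 1.89/1.68 = 1.13. The SAP's power figures are not needed here.

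**2. Arithmetic of a fading gap.** Let m = (2.22 + 1.89 + 1.68)/3 = 1.93 and let a share p of each arm's deviation from m persist. With no effect, the Group × Time ratio for Group 1 vs 3 is

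R(p) = {[m + p(2.22 − m)]/[m + p(1.68 − m)]} / (2.22/1.68).

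At p = 0.5 this is (2.075/1.805)/1.321 = 0.87.

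| Share persisting | 100% | 75% | 50% | 25% | 0% |
|---|---|---|---|---|---|
| Group 1 vs 3 | 1.00 | 0.93 | 0.87 | 0.81 | 0.76 |
| Group 2 vs 3 | 1.00 | 0.97 | 0.94 | 0.91 | 0.89 |

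**3. Chance gap, by correlation.** Two-arm null trials were simulated with 8 × 10 children per arm, baseline mean (2.22 + 1.68)/2 = 1.95 and a 35% fall in both arms. There were 40,000 trials per setting, kept if the gap was within 0.05 of 2.22 − 1.68 = 0.54.

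| CVB 0: correlation | .17 | .26 | .34 | .44 | .52 | .65 |
|---|---|---|---|---|---|---|
| Group × Time ratio | .794 | .815 | .839 | .864 | .887 | .919 |

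| CVB .182: correlation | .18 | .28 | .35 | .45 | .53 | .66 |
|---|---|---|---|---|---|---|
| Group × Time ratio | .817 | .846 | .855 | .882 | .897 | .930 |

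Adjusted for the child's pre count, the ratio was 0.992–1.034. For Group 2 (gap 0.21) the Group × Time ratio was 0.90–0.97. The SD of the chance gap was 0.40–0.50, so 0.54 is 0.54/0.50 = 1.1 to 0.54/0.40 = 1.35 SD: chance is plausible but not established.

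**4. Models fitted directly.** Three arms, 24 × 10 children, negative binomial GLMM with school random intercept and a COVID-19 covariate, no season term; 400 null trials per setting with both gaps within 0.08 of those reported. At correlations of 0.16–0.63, Group × Time for Group 1 gave .790, .820, .870, .923 (CVB 0) and .851, .861, .902, .919 (CVB .182). The adjusted model gave .982–1.006 and .988–1.064. Monte Carlo SE was .009–.013. Without conditioning on the gap, both methods gave 0.99–1.01.

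**5. Precision.** For equal-variance Gaussian data, adjusted variance over change variance is (1 − ρ²)/[2(1 − ρ)] = (1 + ρ)/2: 0.65, 0.75 and 0.85 at ρ = 0.3, 0.5 and 0.7. The fitted count models (900 unconditional trials per setting) gave 0.63–0.97 under the null and 0.69–0.98 under the planned effect, a gain of 3–37% and 2–31%, with little gain near correlation 0.6.

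**6. The opposite case.** If true means of 2.22 and 1.68 are lasting, Group × Time gives 1.00. The adjusted ratio runs from 1.25 at low correlation to 1.09 at high correlation.

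**7. False positives.** Two-sided size was 0.0–1.6% for the model as written and 1.4–2.9% for the adjusted model, against 1.67%. Given the gap, the written test falsely favoured Group 1 in 0.0–1.5% of null trials.

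**The case against.** The strongest reply is that baseline is already in the model. Each arm is compared with its own pre period, so a stable difference drops out. That stands: a reader might infer that baseline is ignored, and the SAP does not support that reading.

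A lasting gap is also credible. Under Protocol D2, 2.e the arm follows from the child's school, with only 8–9 schools per condition, and under 2.d school nurses refer families. If the gap is lasting, change is the right contrast and adjustment penalizes the intervention by about as much as change would flatter it in the other case. The selection argument is weaker than it first looks: eligibility looks back two years, also admits unscheduled primary-care visits and steroid use, and the ED list is one route among several. All of this stands. It does not remove the tilt for a chance gap, which needs no selection, but the documents cannot settle how much persists.

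The rates are unadjusted and ED-only, so the imbalance in the composite is unknown. Replacing a declared primary contrast because of an imbalance already seen is data-driven. Timing matters too: 217 families date from before 13 March 2020 (Protocol B3), and 9 + 9 months takes them to about September 2021, before the SAP's date of June 2022. The documents do not show whether post counts by arm were still unexamined. These points decide the form of the fix: an added analysis, not a substitution.

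**Conclusion.** The point holds in a limited form, with medium confidence. Given the reported gaps, and if they are chance, Group × Time leans toward benefit by an expected factor of about 0.8–0.93 for Group 1 vs control and 0.90–0.97 for Group 2. At the SAP's CVB of 0.1820 the Group 1 figure is 0.82–0.93. On the log scale this is ln 0.93/ln 0.43 = 9% to ln 0.79/ln 0.43 = 28% of the planned effect. The contrast is also less precise than the adjusted one by the amounts in step 5. All of this rests on the assumed correlation and variance structure.

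Three stronger readings are not supported:

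- **The written test produces too many false positives.** None of the runs shows this. It was checked only for the model as written, whose standard errors are wide for a within-child contrast because no child-level effect is named.
- **The declared primary contrast is wrong and must be replaced.** It is unbiased over randomizations and exactly right if the gap lasts.
- **The planned 0.43 is itself a baseline artefact.** The cited study did start unbalanced (2.0/1.3 = 1.54), and its post-only ratio is 0.55/0.85 = 0.65. That is the right contrast only if its gap was wholly transient, which nothing in the documents shows.

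**What to change.** Before post counts by arm are examined, amend the SAP to add one prespecified analysis:

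- **Outcome and model:** the 9-month post count, from the same count GLMM (three groups, school random effect, season and COVID-19 terms).
- **Added covariate:** the child's 9-month pre count, for example log(count + 1), used only as a covariate and not also as an outcome level.
- **Inference:** small-cluster degrees of freedom, given 24 schools and the 1.4–2.9% size seen without them.

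Report it beside the declared Group × Time contrast and state in advance how disagreement will be read. Benefit seen only in Group × Time is compatible with a fading baseline gap. Benefit missing only in the adjusted model is compatible with a lasting one.

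The sponsor may choose to make the adjusted model primary; if so, record that the decision followed knowledge of arm-level baseline rates. If post counts by arm have already been seen, label the added analysis post hoc.

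The cost is a SAP amendment and a little more analysis. No new data are needed, since the pre count is already to be obtained. The adjusted model's own possible error, against the intervention if the gap is lasting, is the reason to report both.

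### The primary count model names a school effect but no child or dispersion term, so the standard error of the main test is likely to be wrong; the distribution, link and effect scale are also left open.

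*SAP*

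**What the plan says.** SAP Aim 1 sums each child's asthma admissions and ED visits. It then states "Our primary endpoint is the change in mean rate of ED/hospitalization in 9 months before to 9 months after RVA Breathes across groups" and adds that "our main outcome is change in healthcare utilization at the individual level as an average of individuals".

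The test is the interaction of group with time (pre, post) in a GLMM. School is the only random effect named. Time is called a within-subject factor, but no child effect, dispersion term or person-time offset is written down.

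On distribution, Aim 1 says "GLMM models will be fit to multiple types of dependent variables including, Gaussian/Normal, Binomial, Poisson and Negative Binomial" and does not say which applies to the primary count. Aims 2 and 3 refer to "utilizing the proper distribution and link functions for the outcome variable examined"; no link is named for the primary outcome. The Sample size section says "using a Poisson model for analyses, we would use a CVB (between-cluster coefficient of variation) instead of ICC" and expresses effects as reductions of 72% and 35%.

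The SAP's opening paragraph has the data explored before testing and lets the analysts "consider transformation as appropriate", with no rule and no exemption for the primary outcome.

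For baseline rates, Group 1 "had a 9-month ED visit rate of 2.22 visits"; Groups 2 and 3 are at 1.89 and 1.68. Protocol A2 and C1 speak only of greater reductions and fix no scale.

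**The concern.** Each child contributes two counts. Two kinds of extra variation are likely: some children are persistently high users, and a given child's underlying rate moves between one nine-month period and the next. A school effect captures neither. Poisson leaves out the second kind, so its standard error is too small. Negative binomial with no child term treats the two counts of one child as independent, so its standard error is too large. The first error makes a false claim of benefit more likely; the second may hide a real one.

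The unstated effect measure is a related gap. With unequal baselines, equal falls in visits and equal percentage falls are different null hypotheses, so the plan does not settle which one the primary test addresses.

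**Working it through.** **Inputs.** From the SAP's Sample size section: baselines 2.22 (Group 1), 1.89 (Group 2), 1.68 (Group 3); reductions 72% and 35%; alpha .0167 (taken as two-sided, critical value 2.393); 240 evaluable children, so 80 per arm. Assumed, because the documents give no values: child variance s² of 0 to 1 and occasion variance v of 0 to 0.5, each for a gamma multiplier with mean 1.

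**1. The plan's own figures.** 240/(1 − 0.20) = 300 reproduces. (2.0 − 0.55)/2.0 = 0.725 and (1.3 − 0.85)/1.3 = 0.346 agree with the stated 72% and 35%. The power figures of 14%, 97% and 88% could not be reproduced at alpha .0167 with 8 schools of 10 per arm; the closest variant missed by about 5 points. That is a separate matter. It bears on this point only as follows: if both active arms fall 72%, a ratio-scale interaction for Group 1 v 2 is at its null with power 1.67%, so on that assumption the 14% is not on the ratio scale.

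**2. Variance of the contrast.** The contrast is the log ratio of post/pre rate ratios. Let S be the sum of the reciprocals of the four group-by-period means. To first order:

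- true variance = [S + 4v(1 + s²)]/80
- Poisson, no child or dispersion term, reports S/80
- negative binomial, no child term, has dispersion (1 + s²)(1 + v) − 1 = s² + v(1 + s²), so it reports [S + 4s² + 4v(1 + s²)]/80

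A child effect shared by both counts cancels from the true variance when v = 0. Poisson is short by 4v(1 + s²)/80; negative binomial is over by 4s²/80.

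**3. Rejection under equal percentage falls, Group 1 v 3.** For a common 35% fall, S = 1/2.22 + 1/1.443 + 1/1.68 + 1/1.092 = 2.654. With s² = 0.5 and v = 0.25 the true sum is 2.654 + 1.5 = 4.154.

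- Poisson: the effective critical value is 2.393 × √(2.654/4.154) = 1.913, so it rejects 5.6%.
- Negative binomial: 2.393 × √(6.154/4.154) = 2.913, so it rejects 0.36%.

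The same steps for other values (S = 4.780 for a common 72% fall):

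| s² | v | Poisson, 35% fall | Poisson, 72% fall | NB without child term, 35% | NB without child term, 72% |
|---|---|---|---|---|---|
| 0 | 0.25 | 4.1% | 3.0% | 1.7% | 1.7% |
| 0.5 | 0 | 1.7% | 1.7% | 0.15% | 0.44% |
| 0.5 | 0.25 | 5.6% | 3.7% | 0.36% | 0.60% |
| 0.5 | 0.5 | 10.1% | 6.1% | 0.54% | 0.73% |
| 1 | 0.5 | 13.1% | 7.7% | 0.25% | 0.39% |

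Simulated trials of this kind, with no school effect, gave about 3–12% for Poisson with v of 0.25–0.5, and 0.0–0.9% for negative binomial with no child term.

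**4. Power at the planned effects, Group 1 v 3.** The effect is log(0.28/0.65) = −0.842. S = 1/2.22 + 1/0.6216 + 1/1.68 + 1/1.092 = 3.570. Take s² = 1 and v = 0.

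- The true standard error is √(3.570/80) = 0.211, giving power Φ(0.842/0.2113 − 2.393) = 94%.
- Negative binomial with no child term reports √(7.570/80) = 0.308, giving Φ((0.842 − 2.393 × 0.3076)/0.2113) = 69%. Simulation gave 70%.

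**5. Scale.**

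- Common 35% fall: 0.35 × (2.22 − 1.68) = 0.189 visits in favour of Group 1, yet a ratio of ratios of 1.
- Common fall of 1.0 visit: (1.22/2.22)/(0.68/1.68) = 1.36 in favour of control, yet a difference of 0.
- Planned effects, unrounded reductions: difference in change 2.22 × 0.725 − 1.68 × 0.346 = 1.03 visits; ratio of ratios 0.275/0.654 = 0.42. Both favour the intervention.
- With control falling 35% (0.588 visits), Group 1 does better on the difference scale once its fall exceeds 0.588/2.22 = 26.5%, and better on the ratio scale once it exceeds 35%. Direction conflicts only between those values.
- Significance can differ more widely. In simulations with 8 schools of 10 per arm at the planned effects, the two scales gave different significance results in 13–31% of runs for Group 1 v 3 and 24–41% for Group 2 v 3 (cluster-level tests, child variance 0 to 1).

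**The case against.** The best defence is that Aim 1 speaks of within-person change and a within-subject time factor, so a competent analyst would include a child term, and that negative binomial is already on the list. The intention may well be there. But a fixed time factor does not model the correlation between a child's two counts, the only random effect written is school, and negative binomial without a child term overcorrects.

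It is also right that a child effect alone does not inflate the Poisson test; occasion-level variation is needed, and its size is assumed here.

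Three stronger readings are tempting, and the documents do not support them.

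- A reader might infer that the endpoint is an absolute change that contradicts a ratio model. The sentence about an average of individuals can equally mean that the child, not the school, is the unit of inference in a school-randomised trial (Protocol D2, 2.e), and a change in mean rate fits either scale. The summed count, the Poisson model and the percentage reductions already lean towards a ratio. The list of families is written for outcomes of several types, not clearly as a menu for the primary one.
- A reader might infer that the scale will be chosen after seeing results by arm. The SAP describes general descriptive work before testing and says nothing about looking by arm or picking among results, so no error rate can be attached to that.
- A reader might cite a common 72% fall, where an absolute-change test would often reject although the percentage falls are equal. That needs control to fall 72% against a planned 35%, and with school clusters the rejection rate is about 8–12%. It would also be detecting a true absolute gap (0.389 visits), not making an error on its own scale.

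**Conclusion.** The concern holds as a specification fault in the primary model. As written, a Poisson fit would reject about 3–12% of the time at nominal 1.67% if occasion variance is 0.25–0.5, and hold its level if that variance is zero. Negative binomial with no child term would be too conservative whenever children differ persistently. Neither variance is given in the documents, and the calculations leave out school effects and the seasonality and COVID-19 covariates.

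The open scale is a secondary part of the point. The nulls differ at the stated baselines, but at the planned effects both scales favour the intervention, and direction conflicts only over a narrow range of Group 1 falls. The log link is the usual default, not something the SAP states. The baselines are ED visits only, so the imbalance in the composite with admissions is unknown.

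**What to change.** In SAP Aim 1, for the primary outcome:

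- Specify the untransformed count of ED visits and admissions, a negative binomial GLMM with log link, a log person-time offset, and a child random intercept in addition to the school effect.
- Define the effect as the ratio of post/pre rate ratios, active v control, which fits the Poisson model and percentage reductions in the Sample size section. Reword the two endpoint sentences to match. Under a log link with a random intercept this ratio is the same for a child and for the mean rate, so the two sentences can be reconciled.
- Exempt the primary outcome from the transformation clause in the opening paragraph.
- Report the absolute difference in change as a supporting estimate without a separate test.
- Name Poisson with child-clustered standard errors as a sensitivity analysis.

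The cost is SAP wording and one extra estimate, with no new data. Standard errors will be somewhat wider than under plain Poisson. For example, with s² = 0.5 and v = 0.25 at the planned effects for Group 1 v 3, √((3.570 + 1.5)/80) = 0.252 against 0.211, and power is Φ(0.842/0.2517 − 2.393) = 83% instead of 94%. That is uncertainty which plain Poisson would not show.

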2.d.i. Changes to recruitment and consent process due to COVID-19: Recruitment in the community will be limited to remote options (e.g., as a part of virtual newsletters or emailed flyers). School nurses will still call potentially eligible families, we will still receive lists of children seen at VCU and BSHS, and letters will be mailed from provider offices. Families will be screened using our IRB approved screening materials. If a family screens eligible, the caregiver will be told that, "Due to COVID-19 and recommendations from the Health Department, and for the safety of families and our staff, we are now conducting RVA Breathes remotely. This means that the consent process and all research and intervention sessions will be conducted over the phone or video." A phone or video session will then be scheduled to conduct the verbal consent process and complete baseline measures. Questions will be asked to the parent and then to the child separately. If the child is not available or is not comfortable answering questions, these will be marked as missing data. IRB has approved a waiver of documentation of consent for parents in RVA Breathes. This is for their participation in the study and for the participation of their child. We will instead obtain verbal consent and will document in our research record using a consent documentation form that records that consent was given, what day/time it was given, and who was present for the discussion. We are also approved to waive child assent, which is recorded on the consent documentation form.

2.e Randomization Method and Blinding

Families will be randomized at the school level. In consultation with RPS, we will match elementary schools based on demographics and location, and whether school nurses travel among schools; 8-9 schools will be included in each condition. We will use a block randomization scheme. After the baseline session is complete, the project coordinator will randomize the family to one of the 3 conditions based on the child's school. Given the nature of our program, it will not be possible to blind participants or study staff to their condition. Analysts collecting data from insurance companies will be blind to condition.

2.f Risks and Benefits

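### The only random effect the SAP names is for school; read as an intercept it cancels from Group x Time, so the primary standard error omits school-to-school variation in change

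*SAP*

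**What the plan says.** Protocol section 2.e states "Families will be randomized at the school level" and that "8-9 schools will be included in each condition". In SAP Aim 1 the endpoint is defined thus: "Our primary endpoint is the change in mean rate of ED/hospitalization in 9 months before to 9 months after RVA Breathes across groups". The model has a fixed Group factor and "will also include a random effect for the cluster (school". For the longitudinal analysis it is extended by "inclusion of a within-subject factor (Time [pre, post]) and the interaction between Group and Time variables", and the SAP gives the purpose of that extension: "The inclusion of the interaction terms allows for a formal test of differing courses between the groups over time". Sine and cosine terms for season and a before/after COVID-19 indicator enter as covariates.

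The SAP does not say whether the school effect is an intercept, a slope or both. It speaks of within-person change but names no child random effect. It also names no school x Time effect, residual covariance, robust variance or degrees-of-freedom rule. The count distribution is left open: "GLMM models will be fit to multiple types of dependent variables including, Gaussian/Normal, Binomial, Poisson and Negative Binomial". Poisson is mentioned as the model only in the Sample size text, which gives between-school coefficients of variation (CVB) of .1331, .1820 and .0502 for the three pairwise comparisons.

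**The concern.** Because whole schools are assigned to arms, Group x Time compares average changes between sets of schools. Its error term therefore has to contain the variation between schools in change. A school intercept describes something else: how far a school lies above or below average in both periods. That part is removed when pre is subtracted from post.

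The plan thus appears to allow for clustering, but on the natural reading it does not do so for the one contrast that carries the primary test. If schools differ in how much their children improve, the Poisson analysis treats that variation as if it did not exist. The interval is then too narrow, and a true null is rejected more often than planned.

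The absence of a child effect matters too. Under a Negative Binomial model, stable differences between children are then absorbed into the dispersion and counted as noise in the change, which pushes the standard error the other way.

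**Working it through.** **The plan's own figures.** 240/0.8 = 300 and .05/3 = .0167, so the sample size and alpha reproduce. The stated powers (14%, 97%, 88%) do not reproduce at the stated inputs: a log-scale comparison of changes including CVB, 8 schools x 10 children per arm, two-sided .0167, gives about 1%, 90% and 92%. That is a separate matter and nothing below depends on it.

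**Step 1: cancellation.** With a log link and school intercept b, the log mean for a school is (fixed part, pre) + b before and (fixed part, post) + b after. The difference does not contain b. In a balanced Poisson model the Group x Time standard error is then the square root of the sum of 1/(total count) over the four arm-by-period cells, whatever the variance of b. Four Poisson school-intercept models fitted to simulated data gave an estimate and standard error equal to this closed form to four decimals (for example .3054, SE .1740). With the season and COVID-19 covariates the cancellation is approximate.

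**Step 2: size under Poisson, Group 1 vs Group 3.** Inputs from SAP Sample size: 9-month baseline rates 2.22 and 1.68; 24 schools of 10, hence 8 schools and 80 children per arm; alpha .0167, taken as two-sided (critical value 2.393). The null is set as the SAP's 35% control reduction in both arms.

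- Model variance = 1/(80 x 2.22) + 1/(80 x 2.22 x .65) + 1/(80 x 1.68) + 1/(80 x 1.68 x .65) = .0056 + .0087 + .0074 + .0114 = .0332 (unrounded sum).
- Actual variance = .0332 + 2 x tau²/8, where tau is the SD between schools of the log change (**assumed**; not in the documents).
- SE ratio = sqrt(actual/model). Type I error = 2 x (1 − Phi(2.393/ratio)).

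| tau (assumed) | added variance | SE ratio | type I error |
|---|---|---|---|
| .05 | .0006 | 1.009 | .0177 |
| .18 | .0081 | 1.115 | .0319 |
| .30 | .0225 | 1.295 | .0647 |

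The error rate doubles at tau of about .19.

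**Step 3: link to the SAP's CVB.** Suppose CVB is total school variation in each period, with pre-post correlation r (assumed). Then tau = CVB x sqrt(2(1 − r)).

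| r (assumed) | G1 vs G3, CVB .182: tau | type I error | G2 vs G3, CVB .0502: tau | type I error |
|---|---|---|---|---|
| 0 | .257 | .051 | .071 | .0187 |
| .5 | .182 | .032 | .050 | .0177 |
| .8 | .115 | .022 | .032 | .0171 |
| .9 | .081 | .020 | .022 | .0169 |

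**Step 4: Negative Binomial with a school intercept and no child effect** (simulation, 6,000 trials per setting, true null, child log-rate variance assumed).

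| child variance | mean model SE | empirical SD at tau .05/.18/.30 | type I error |
|---|---|---|---|
| .5 | .247–.250 | .184/.203/.239 | .001/.002/.012 |
| .2 | .210–.212 | .185/.207/.242 | .007/.016/.035 |

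**Step 5: does the remedy work?** Simulation with 24 schools x 10 children, 35% reduction in all arms, 10,000 trials per tau; child variance .5 and school intercept SD .13 assumed. The model was fitted in an equivalent form with child and school intercepts conditioned out. Type I error for Group 1 vs Group 3:

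| Analysis | tau .05 | tau .18 | tau .30 |
|---|---|---|---|
| Poisson, school intercept only, z | .017 | .033 | .070 |
| plus school x Time effect, z | .015 | .022 | .031 |
| plus school x Time effect, t on 21 df | .008 | .012 | .020 |
| school-level t test on log change, 14 df | .016 | .014 | .016 |

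The extra term is not enough without the t reference. The school x Time variance was estimated at about zero in 70%, 43% and 15% of trials.

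**The case against.** The strongest reply is that harm needs three things together, none of which the documents establish: an intercept-only school effect, a Poisson model and a material tau. The SAP is silent on the form of the effect and does not choose between Poisson and Negative Binomial, and five of the six Negative Binomial error rates in Step 4 lie below nominal. CVB is not described as variation in change. With a pre-post correlation of .8 or more the Group 1 vs Group 3 error is .022 or less, and tau = .30 exceeds even the .257 obtained at r = 0. The COVID-19 and season covariates will also remove some of the variation between schools in change.

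Most of this stands as a limit on size: tau is unknown, .30 is only an illustration, and the direction depends on the distribution. It does not remove the point. A primary model whose standard error can err in either direction, depending on choices left open, needs to be specified. The covariates deal with calendar exposure only, not with schools that differ for other reasons.

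A second objection is that the 21-df reference is conservative at small tau (.008), while the school-level t test is better calibrated throughout. That is correct. The school-level test costs more power, so either could reasonably be primary.

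**Conclusion.** The concern holds. As written, SAP Aim 1 gives the primary Group x Time test no term for school-to-school variation in change, although schools are randomized. Under Poisson the standard error is too small whenever such variation exists. The effect is negligible at tau .05 and roughly doubles the Group 1 vs Group 3 error rate at tau near .19. For Group 2 vs Group 3 it is negligible at the SAP's CVB. Under a Negative Binomial with no child effect the test is more likely to be conservative.

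This rests on reading the school effect as an intercept, on a pre/post layout of 8 schools x 10 children per arm, and on assumed values of tau and of the child variance. The weakness should be corrected, but its practical size cannot be settled from the documents; confidence is medium.

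**What to change.** In SAP Aim 1, write out the random effects of the primary count model in full: a child intercept, a school intercept and a school x Time effect. Naming the count distribution in the same sentence would settle the direction of any remaining error. Base tests and intervals on a t reference with school-level degrees of freedom: 24 − 3 = 21 for the three-arm model, or 8 + 8 − 2 = 14 for a pairwise school-level analysis. State that these degrees of freedom are kept when the school x Time variance is estimated at zero. Name a school-level analysis of log change as the alternative or check.

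The work is SAP wording and standard software options. The cost is power. For Group 1 vs Group 3, with effect log(.28/.65) = −.842 and Poisson variance .0446:

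| Reference | tau 0 | tau .05 | tau .18 |
|---|---|---|---|
| z, Poisson SE only | 94% | – | – |
| t, 21 df | 91% | 90% | 85% |
| t, 14 df | 88% | 87% | 81% |

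At tau .05 nearly all of the loss comes from the t reference. In simulation the school-level t test on log change had 83% power at tau .05 and 77% at tau .18.
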